9.7.3.2 Patient-Reported Outcomes (PRO)

The Haemo-QoL-A questionnaire is a validated hemophilia-specific health-related quality of life questionnaire for adults ([Rentz, 2008](#)). It consists of 41 questions covering six domains (Physical Functioning, Role Functioning, Worry, Consequences of Bleeding, Emotional Impact and Treatment Concerns). Items are answered on a 6-point Likert-type scale, ranging from 0 (None of the time) to 5 (All of the time). Higher scores mean better health-related quality of life or less impairment for a particular subscale ([Haemo-QoL Study Group, 2017](#)).

The EQ-5D-5L instrument is a self-reported questionnaire designed to measure general health status ([The EuroQol Group, 1990](#)) ([Brooks, 1996](#)). The EQ-5D-5L is composed of 2-parts: a descriptive system that assesses 5 levels of perceived problems (mobility, self-care, usual activities, pain/discomfort, and anxiety/depression) in 5 dimensions and the EQ visual analogue scale (EQ VAS) assessment for overall health.

The Work Productivity and Activity Impairment plus Classroom Impairment Questions: Hemophilia Specific (WPAI+CIQ:HS) instrument is designed to measure the effect of disease symptom severity on work productivity and classroom productivity (if applicable) ([Recht, 2014](#)). The WPAI+CIQ:HS questionnaire yields scores related to work/classroom absenteeism, reduced on-the-job effectiveness, overall work/classroom impairment, and activity impairment. WPAI+CIQ:HS outcomes are expressed as impairment percentages, with higher numbers indicating greater impairment and less productivity ([Reilly, 2002](#)).

The Patient Reported Outcomes, Burdens, and Experiences (PROBE) questionnaire is designed to investigate and directly probe patient perspectives on outcomes they deem relevant to their life and care. PROBE aims to develop a new global tool to enhance the direct patient-voice in health care decision-making ([Chai-Adisaksopha, 2017](#)).

Details (including sample copies where applicable) for each of the PRO instruments are provided in the Investigator Site File Binder.

9.7.4 Immunogenicity

Immunogenicity assays will be performed on plasma and PBMCs. The assays will include detection of anti-AAV5 capsid and anti-FVIII total antibodies, as well as determination of neutralizing antibodies against FVIII (FVIII inhibitors) and against the AAV5 capsid (transduction inhibitors, TI). FVIII inhibitors will be assessed using the chromogenic Bethesda assay with Nijmegen modification. Any abnormality of the liver parameters will lead to a retrospective immunogenicity assessment to evaluate FVIII- and capsid-specific cellular immunogenicity. FVIII- and capsid-specific cellular immunity will be assessed by stimulated cytokine secretion using an ELISpot assay performed on collected PBMCs.

9.7.5 Pharmacodynamics

The FVIII protein concentration and activity level as measured by a validated immunoassay and by a validated FVIII activity assay, respectively, will be used for plasma profiles; FVIII protein and activity will be used to determine PD parameters.

9.7.6 Pharmacokinetics

Sparse FVIII activity assessments, prior to BMN 270 administration, will be collected to estimate each subject's half-life of replacement FVIII concentrate used for prophylaxis. Samples will be drawn immediately prior to recombinant FVIII concentrate infusion (between Day -2 and Day -7), 3 hours (+/- 30 minutes) post-FVIII infusion, and 24-52 hours post-FVIII infusion. If supported by the data, sparse samples together with established population pharmacokinetic models will be used to estimate an individual subject's FVIII activity clearance (CL) value. Individual subject CL estimates may then be evaluated against post-BMN 270 FVIII activity levels to determine if an association exists between an individual's FVIII activity CL value and FVIII activity levels achieved with BMN 270. For subjects receiving emicizumab, pharmacokinetics assessment is optional.

9.7.7 Exploratory Assessments

Blood samples will be collected from subjects at the time points indicated in the Schedules of Events to evaluate biochemical, molecular, cellular, and genetic/genomic aspects relevant to hemophilia A, coagulation, and/or AAV gene transfer, and to develop assays used for these evaluations. Subjects may choose to opt out of the exploratory genetic/genomic research being done to study or try to discover genes that are not yet known to be associated with hemophilia A.

All biomarker samples collected in this study may be used for exploratory biomarker research, including evaluation of additional biomarkers not specifically listed in the protocol. In addition, samples collected for other purposes in this study may be used for exploratory research once testing for the primary purpose has been completed.

9.7.7.1 Optional Liver Biopsy

Subjects electing to undergo an optional liver biopsy are required to consent to the procedure and collection of tissue in the study ICF. The analysis of the optional liver biopsy is considered exploratory. Patients who elect to proceed will have a liver biopsy performed around Week 26, Week 52, and/or during Years 2-5. Additional liver biopsies at times deemed to be clinically relevant (eg, decreasing FVIII at a time of increased ALT) may be pursued. Subjects will be asked to consent to the procedure for each liver biopsy performed during the study.

Subjects who consent to the procedure will have a liver biopsy via either transjugular or percutaneous (ultrasound-guided) route, according to the standard procedures of the institution. Two tissue cores will be harvested in the context of the optional liver biopsy. Subjects will be required to observe an 8-hour fasting period before the procedure.

Within 24 hours prior to the biopsy being performed, subjects must have a documented FVIII activity level of ≥ 50 IU/dL (or higher, depending on local guidelines and/or investigator discretion). FVIII activity levels for this purpose should be assessed at the local laboratory within 7 days before the biopsy and again on the day the biopsy, prior to the procedure. As needed, subjects may be treated with additional exogenous FVIII replacement products in order to increase their FVIII activity levels to an appropriate level, under the supervision/instruction of the investigator, to ensure the safety of the subject during the procedure. This exogenous FVIII usage (if performed) should be recorded in the eCRF FVIII infusion pages under the category “Surgery/Procedure”.

Details on required procedures for the optional liver biopsy are outlined in [Table 9.1.5](#). Subjects consenting to participate to the optional liver biopsy will undergo pre-biopsy assessments at least 28 days before the procedure, as follows:

- Physical examination
- Hematology, coagulation, chemistry assessments
- Liver tests
- Liver ultrasound (subject should fast at least 8 hours prior to ultrasound)
- FibroScan

Subjects consenting to participate to the optional liver biopsy will undergo pre-biopsy assessments at least 7 days before the procedure, as follows:

- Local FVIII activity level assessment
- Pre-biopsy consultation (with hepatologist and/or radiologist)

On the day of the biopsy, brief physical examination and liver and blood tests should be performed before the procedure (including hematology, coagulation, and chemistry). FVIII activity assessment should also be performed to ensure the subject has sufficient FVIII activity to protect against procedure-related bleeding (as discussed above). LT assessment and a whole blood draw for PBMC collection should be performed on the biopsy day or \pm 1 week from the biopsy day.

The optional liver biopsy should be performed in the morning if feasible, and the biopsy procedure and follow-up care should be done according to the local standard of care.

Additional details for handling the biopsy specimens are provided in the Study Reference Manual.

Following completion of the biopsy, the subject should remain under observation in the clinic for at least 4-6 hours. Overnight post-procedure observation may be done at the investigator's discretion and/or according to local guidelines.

Clinically significant findings reported from the histopathological analysis of the biopsy sample are subject to AE reporting (Section 10). Such findings should be further assessed and followed as clinically appropriate to manage the subject's medical care. A hepatologist and/or other specialist clinicians should be consulted if required. In the event that fibrotic changes are observed on the biopsy sample, additional liver ultrasound, FibroScan and/or Enhanced Liver Fibrosis (ELF) testing (as regionally available and/or approved by HA) may be considered at the discretion of the investigator and/or hepatologist.

9.7.8 Safety Variables

Safety in this study will be determined from evaluation of AEs, clinical laboratory assessments with a particular attention to the liver function, vital signs assessments, physical examinations, and immunogenicity. In case of a safety concern, additional unscheduled laboratory tests may be performed locally (at the Investigator's discretion) in order to facilitate timely and appropriate clinical management decisions; where possible, a matched sample for testing at the central laboratory should be collected (using the Unscheduled Visit lab kit) at the same time as the local unscheduled sample

9.7.8.1 Adverse Events

The determination, evaluation and reporting of AEs will be performed as outlined in Section 10.

9.7.8.2 Clinical Laboratory Assessments

The scheduled clinical laboratory tests are listed in Table 9.7.8.2.1. Refer to the On Site File Binder for instructions on obtaining and shipping samples.

Any abnormal test results determined to be clinically significant by the Investigator should be repeated (at the Investigator's discretion) until: (1) the cause of the abnormality is determined; (2) the value returns to baseline or to within normal limits; or (3) the Investigator determines that the abnormal value is no longer clinically significant.

All abnormal clinical laboratory results should be initialed and dated by an Investigator, along with a comment regarding whether or not the result is clinically significant. Each clinically significant laboratory result should be recorded as an adverse event.

The diagnosis, if known, associated with abnormalities in clinical laboratory tests that are considered clinically significant by the Investigator will be recorded on the AE eCRF.

In case of a safety concern, additional unscheduled laboratory tests may be performed locally (at the Investigator's discretion) in order to facilitate timely and appropriate clinical management decisions; where possible, a matched sample for testing at the central laboratory should be collected (using the Unscheduled Visit lab kit) at the same time as the local unscheduled sample.

Table 9.7.8.2.1: Clinical Laboratory Tests

Blood Chemistry	Hematology	Urine Tests	Coagulation Screen including:
Albumin	Hemoglobin	Appearance	APTT
BUN	Hematocrit	Color	PT/INR
Calcium	WBC count	pH	TT
Chloride	RBC count	Specific gravity	
Total cholesterol	Platelet count	Ketones	Complement Panel
CPK	Differential cell count	Protein	C3
Creatinine	RBC indices (MCV and MCH)	Glucose	C3a
CRP		Bilirubin	C4
Glucose		Nitrite	Bb
Phosphorus		Urobilinogen	sC5b-9
Potassium		Hemoglobin	
Total protein			Other Tests:
Sodium			ABO blood typing*
Uric Acid			

BUN, blood urea nitrogen; CPK, creatinine phosphokinase; CRP, C-reactive protein; PT, prothrombin time; APTT, activated partial thromboplastin time; RBC, red blood cell; WBC, white blood cell; TT, thrombin time; INR, international normalized ratio; MCV, mean corpuscular volume; MCH, mean corpuscular hemoglobin.

*ABO blood typing assessment should be performed at Screening.

In addition to scheduled clinical laboratory assessments, a fasting blood lipid panel (including triglycerides, total cholesterol, HDL cholesterol, and LDL cholesterol) and FibroTest will be assessed at the BMN 270 infusion visit. Subjects will fast for at least 8 hours prior to pre-infusion laboratory sampling on the day of the infusion visit.

In case of a Grade 2 or higher hypersensitivity or adverse drug reaction, a safety assessment including physical examination and vital signs will be performed and additional blood samples will be collected within 1 hour, and 8-24 hours following the hypersensitivity reaction for assessment of complement (C3, C3a, C4, Bb, and sC5b-9) and tryptase.

Additional samples will be collected at the 1 hour and 8-24 hour time points and, if possible, 1 week after the event for an optional, exploratory CBA to assess inflammatory biomarkers and plasma cytokine levels. Inpatient observation can be extended and additional blood samples can be collected if deemed necessary at the discretion of the Investigator and Medical Monitor.

At applicable sites, certain study assessments may be performed by an MN professional at the patient's home or another suitable location, such as their school or office, to improve access and convenience for patients participating in the study. The Sponsor may select a healthcare company that will be responsible for providing MN services for participating sites (the MN vendor). The MN vendor is responsible for ensuring that all MN professionals are licensed, qualified, and in good standing, as per applicable regulations, and that appropriate background checks have been performed. If the investigator at a participating site determines that MN services are appropriate for a patient and the patient gives written informed consent to participate in MN visits, the MN network will communicate with the patient and the patient's site. MN visits will be allowed at the visits indicated in the Schedules of Events. Unscheduled visits may also be conducted by MN as appropriate.

9.7.8.3 Liver and Hepatitis Testing

Subjects will be screened for evidence of previous or active hepatitis B or hepatitis C infection at Screening; hepatitis B screening should include HBsAg, HBsAb, and HBcAb. Subjects with documented results showing an absence of active hepatitis B or hepatitis C infection (as measured by negative surface antigen or DNA for hepatitis B or negative RNA testing for hepatitis C) 30 days prior to providing signed informed consent do not need to repeat those tests during the screening period.

Evidence of ongoing hepatitis B or hepatitis C infection is exclusionary. Subjects with a history of hepatitis B or hepatitis C infection prior to study entry will be tested for hepatitis B and hepatitis C reactivation at the timepoints listed in [Table 9.1.6](#). Subjects with a history of hepatitis B or hepatitis C will be asked for information about the treatments received as part of their medical history assessment at Screening.

A liver ultrasound/FibroScan and liver tests (LTs) during Screening will identify any significant hepatic dysfunction.

Where a biopsy has been taken for safety-related reasons or was available from a past procedure, the Sponsor may request the biopsy information to help evaluate the impact of BMN 270 on the liver. The Sponsor may request that slides from a liver biopsy be made available for additional histopathological review.

LTs will be monitored on a regular basis; at each time point, the following LTs should be assessed:

Table 9.7.8.3.1: Liver Tests

Liver Tests (LTs)			
Alkaline Phosphatase	AST (SGOT)	Total Bilirubin	LDH
ALT (SGPT)	Direct Bilirubin	GGT	

ALT, alanine aminotransferase; AST, aspartate aminotransferase; GGT, gamma-glutamyltransferase; LDH, lactate dehydrogenase; SGOT, serum glutamic-oxaloacetic transaminase; SGPT, serum glutamic-pyruvic transaminase

Elevated ALT levels (above the upper limit of normal range) should be evaluated according to the following plan (note that these evaluations may indicate additional testing of LTs and FVIII levels at unscheduled visits; these unscheduled laboratory tests may be completed by a mobile nursing professional at sites where the use of MN services has been approved):

Table 9.7.8.3.2: Evaluation of ALT Elevations

ALT Level	Work-Up
$\geq 1.5x$ Baseline - $<2x$ Baseline	
 Continue to monitor LTs and FVIII per protocol (repeat within 24-72 hours if next protocol scheduled visit is >24-72 hours from the time of the reported ALT elevation) Consider evaluation to rule out alternative etiology (eg, concomitant medications, viral or autoimmune hepatitis, alcohol use, recreational drug use, special diets, strenuous exercise, prior and/or concurrent illnesses, exposure to environmental and/or industrial chemicals, etc.) (refer to Table 9.7.8.3.3) If ALT is $>$ ULN or $> 2x$ baseline in 2 consecutive assessments within 24-72 hours and alternative etiologies have been ruled out, start oral corticosteroids upon consultation with the Medical Monitor (refer to Section 9.4.8.2) Consider liver biopsy at the discretion of the Investigator or Medical Monitor
$\geq 2x$ Baseline or $>$ ULN - $<3x$ ULN	
 Repeat LTs and FVIII within 24-72 hours Continue to monitor LTs weekly until ALT is stable or improving Evaluate and rule out alternative etiologies (as above) Consult with Medical Monitor If ALT is $\geq 2x$ baseline or $>$ ULN - $< 3x$ ULN in 2 consecutive assessments within 72 hours and alternative etiologies have been ruled out, start oral corticosteroids upon consultation with the Medical Monitor (refer to Section 9.4.8.2) Obtain other possibly relevant laboratory evaluations (albumin, PT/INR, CRP, etc.) Obtain complete blood count with differential to assess for eosinophilia Obtain PBMC to evaluate potential immune response (prior to starting oral corticosteroids) If no improvement in 14 days, consider gastroenterology and/or hepatology consult, abdominal workup, imaging (including MRI or ultrasound), and/or liver biopsy as appropriate
$\geq 3x$ ULN	
 Consult with Medical Monitor Evaluate and rule out alternative etiologies (as above) Repeat LTs and FVIII within 24-48 hours, and continue with monitoring of LTs at least twice weekly for as long as the subject's ALT remains $\geq 3x$ ULN

ALT Level	Work-Up
	
 • In the event that ALT or AST is $\geq 3x$ ULN and total bilirubin is $\geq 2x$ ULN, albumin and PT/INR should also be obtained. • If $\geq 3x$ ULN in 2 consecutive assessments within 48 hours, start oral corticosteroids (refer to Section 9.4.8.2) • Obtain other possibly relevant laboratory evaluations (albumin, PT/INR, CRP, etc.) • Obtain complete blood count with differential to assess for eosinophilia • Obtain PBMC to evaluate potential immune response (prior to starting oral corticosteroids) • If no improvement in 14 days, consider gastroenterology and/or hepatology consult, abdominal workup, imaging (including MRI or ultrasound), and/or liver biopsy as appropriate

When ruling out alternative viral or autoimmune hepatitis as part of the elevated ALT workup, the following tests should be performed:

Table 9.7.8.3.3: Viral and Autoimmune Hepatitis Testing

Viral Hepatitis Workup Testing	Autoimmune Hepatitis Workup Testing
Hepatitis A	Smooth muscle antibody
Hepatitis B	Mitochondrial antibody
Hepatitis C	Liver/kidney microsomal antibodies
Hepatitis E	Antinuclear antibody (ANA) HEP-2
Cytomegalovirus (CMV)	
Epstein-Barr virus (EBV)	
Herpes simplex virus (HSV) 1 & 2	

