 - Baseline FVIII activity level – one-stage clotting FVIII assay
 - hFVIII coagulation activity exploratory assay (collected but not tested prior to enrollment)
 - Chromogenic Nijmegen-Bethesda Assay for hFVIII inhibitor level
 - hFVIII protein assay (collected but not tested prior to enrollment)
- hFVIII total antibody (TAb) assay (collected but not tested prior to enrollment)
- Screen for hepatitis B, hepatitis C, and HIV if required (subjects with documented negative results 30 days prior to informed consent being obtained do not need to be retested)
 - Hepatitis B screening should include HBsAg, HBsAb, and HBcAb.
- Blood chemistry, hematology, and coagulation tests (refer to [Table 9.7.8.2.1](#))
 - ABO blood typing assessment should be performed at Screening
- Urine tests (refer to [Table 9.7.8.2.1](#))
- Liver tests (refer to [Table 9.7.8.3.1](#))
- AAV5 TAb Assessment (CDx)
 - If performed during the early Screening period, the CDx AAV5 TAB assessment does not need to be repeated as part of general Screening
- Biomarker testing (including HLA genotyping and FVIII genotyping status)
- Serum for exploratory biomarkers
- Exploratory CK18 and Grp78 assessment

12.2.1 “Smart Rescreening” Visit

Subjects who undergo smart rescreening must complete the rescreening assessments and receive the infusion within 90 days of signing the original consent. Subjects who do not complete dosing within 90 days will be required to re-consent and undergo all screening procedures. Subjects may not undergo smart rescreening more than once.

If a patient has to be screened again because the original assessments have fallen out of the 28 + 14 day period allowed for Screening (refer to Section 12.2), then only the following assessments need to be performed (rather than the full list indicated in Section 12.2) for the patient to be successfully re-screened for the study:

- Vital signs
- Assessment of adverse events and concomitant medications
- Documentation of bleeding episodes and FVIII usage (by either subject or clinical information)
- hFVIII Assays (only the hFVIII inhibitor level (Bethesda assay with Nijmegen modification))
- Blood chemistry, hematology, and coagulation tests (refer to [Table 9.7.8.2.1](#))
- Urine tests (refer to Table 9.7.8.2.1)
- Liver tests (refer to [Table 9.7.8.3.1](#))
- AAV5 TAb Assessment (CDx)

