Screen for Hepatitis B, Hepatitis C, HIV ^d		X			
Screen for COVID-19 (local or central) ^e		X	X		
Blood chemistry, hematology, and coagulation tests ^f		X	X	X	
Fasting lipid panel (blood triglycerides, total cholesterol, HDL cholesterol, and LDL cholesterol)					X
Fasting FibroTest					X

Assessment	Prior to BMN 270 Infusion				BMN 270 Infusion Visit (Day 1) ⁿ
	Screening Day -42 to Day -29	Screening* (Day -28 to Day -1)	Smart Rescreening ^l (Day -28 to Day -1)	Baseline (Day -7 to Day -1) ^m	
Urine Tests ^f		X	X	X	X
Liver Tests ^f		X	X	X	X
AAV5 TAb Assay (CDx) ^g	X	X	X		X
Immunogenicity AAV5 TAb Assay				X	X
AAV5 TI Assay				X	X
IFNg ELISpot				X	
Plasma, PBMC, and RBC collection for exploratory biomarkers ^h				X	
Biomarker testing ^h		X			
Serum for exploratory biomarkers ⁱ		X			X
Exploratory CK18 and Grp78 assessment		X		X	
TGA Assay ^j				X	
Haemo-QoL-A assessment				X	
EQ-5D-5L				X	
WPAI+CIQ:HS				X	
PROBE				X	
PCR of vector DNA in blood, saliva, urine, semen, and stools				X	X
Pharmacokinetics				X ^q	
BMN 270 Infusion					X
Complement Panel ^j				X	X
Hypersensitivity blood assessments ^k					X

* Screening assessments should be performed within 28 days of BMN 270 infusion (and must be performed within 42 days prior to BMN 270 infusion).

^a Complete physical examination should be done at Screening. Brief physical examination may be done at Baseline and at the BMN 270 Infusion Visit.

^b Diaries should be distributed to subjects who have consented to participate in the study and who have been determined to meet all study eligibility criteria.

^c Includes baseline FVIII activity (chromogenic substrate FVIII assay and one-stage clotting FVIII assay), coagulation exploratory assay, chromogenic Nijmegen-Bethesda Assay for hFVIII inhibitor level, and hFVIII protein assay. Baseline activity should be assessed at trough (at least >72 hours after last dose of replacement FVIII therapy, or 5x the known half-life of the FVIII concentrates administered).

^d Patients with documented negative results within the last 30 days do not need to be retested. Hepatitis B screening should include hepatitis B surface antigen (HBsAg), hepatitis B surface antibody (HBsAb), and hepatitis B core antibody (HBcAb).

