^f Visits between scheduled clinic visits may be performed by a mobile nursing (MN) professional at the subject's home or another suitable location (if the subject has given written informed consent to participate in MN visits), or at the site or approved lab facility as a shortened lab draw-only visit. The MN service or site will collect blood samples at these visits. For site lab draw-only visits, sites will contact the subject via phone call or e-mail to collect information regarding adverse events, changes to concomitant medications, bleeding episodes, and FVIII use. For MN visits, the service will collect this information. Unscheduled visits may also be conducted by MN as appropriate.

^g Testing for reactivation of hepatitis B and hepatitis C only for subjects with a past medical history of hepatitis B or hepatitis C prior to study entry.

^h Optional liver biopsy should be obtained within two weeks of Week 26. Additional follow-up liver biopsy will be obtained within two weeks of Week 52. Subjects should fast for at least 8 hours prior to liver ultrasound and optional liver biopsies.

Table 9.1.4: Schedule of Events-Post-Infusion Follow-Up (Year 2-Year 5)

Assessment	Years 2-5*				End of Year Visit				ETV
	Years 2-5	Year 2	Year 3-5	Year 2	Year 3	Year 4	Year 5		
Study Week*	Q12W	Q4W ^g	Q6W ^g	W104	W156	W208	W260		
Physical examination ^b	X			X			X		
Weight ^b	X ^a			X ^a			X ^a		
Assessment of Adverse Events and Concomitant Medications (including review of subject diary for bleeding and hemophilia therapy use)	X	X	X	X	X	X	X		
Vital Signs	X	X ^a	X ^a	X ^a	X ^a	X ^a	X ^a		
Blood chemistry, hematology, and coagulation tests ^c	X ^a	X ^a	X ^a						
Urine Tests ^c	X	X	X	X	X	X	X		
Liver Tests ^c	X	X	X	X	X	X	X		
hFVIII assays ^d	X	X	X	X	X	X	X		
PCR of vector DNA in blood, saliva, urine, and stools	(X) ^e	(X) ^e	(X) ^e						
PCR of vector DNA in semen	(X) ^e	(X) ^e	(X) ^e						
Immunogenicity AAV5 TAb Assay									
AAV5 T1 Assay									
hFVIII TAb	X								
IFNg ELISpot ^a	X ^a								
Plasma, PBMC, and RBC collection for exploratory biomarkers ^f	X								
Serum for exploratory biomarkers ^f	X								
Exploratory CK18 and Grp78 assessment	X	X	X	X	X	X	X		
TGA Assay ^f									
Haemo-QoL-A assessment	X ^a								
EQ-5D-5L	X ^a								

Assessment	Years 2-5*				End of Year Visit				ETV
	Years 2-5	Year 2	Year 3-5	Year 2	Year 3	Year 4	Year 5		
Study Week*	Q12W	Q4W ^g	Q6W ^g	W104	W156	W208	W260		
WPAI+CIQ:HS	X ^a				X ^a			X	
PROBE	X ^a				X ^a			X	

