9.3.2 Exclusion Criteria

Individuals who meet any of the following exclusion criteria will not be eligible to participate in the study:

1. Detectable pre-existing antibodies to the AAV5 capsid. Up to 25% of subjects may have detectable pre-existing AAV5 capsid antibodies, so long as the titer level is below the minimum required dilution (< 20).
2. Any evidence of active infection, including COVID-19, or any immunosuppressive disorder, including HIV infection.
3. Significant liver dysfunction with any of the following abnormal laboratory results:
 - ALT (alanine aminotransferase) > 1.25x ULN;
 - AST (aspartate aminotransferase) > 1.25x ULN;
 - GGT (gamma-glutamyltransferase) > 1.25x ULN;
 - Total bilirubin > 1.25x ULN;
 - Alkaline phosphatase > 1.25x ULN; or
 - INR (international normalized ratio) ≥ 1.4 .

Subjects whose liver laboratory assessments fall outside of these ranges may undergo repeat testing of the entire liver test panel within the same Screening window and, if eligibility criteria are met on retest, may be enrolled after confirmation by the Medical Monitor.

4. FibroScan or prior liver biopsy showing significant fibrosis of 3 or 4 as rated on a scale of 0-4 on the Batts-Ludwig ([Batts, 1995](#)) or METAVIR ([Bedossa, 1996](#)) scoring systems, or an equivalent grade of fibrosis if an alternative scale is used.
5. Evidence of any bleeding disorder not related to hemophilia A.
6. Platelet count of < 100 x 10⁹/L.
7. Creatinine \geq 1.5 mg/dL.
8. Liver cirrhosis of any etiology as assessed by FibroScan or liver ultrasound.
9. Chronic or active hepatitis B as evidenced by positive serology testing (hepatitis B surface antigen [HBsAg], hepatitis B surface antibody [HBsAb], and hepatitis B core antibody [HBcAb]) and confirmatory HBV DNA testing. Refer to the Centers for Disease Control (CDC) table for the interpretation of serological test results in the Laboratory Manual.
10. Active Hepatitis C as evidenced by detectable HCV RNA or currently on antiviral therapy.
11. Active malignancy, except non-melanoma skin cancer.
12. History of hepatic malignancy.
13. History of arterial or venous thromboembolic events (eg, deep vein thrombosis, non-hemorrhagic stroke, pulmonary embolism, myocardial infarction, arterial embolus), with the exception of catheter-associated thrombosis for which anti-thrombotic treatment is not currently ongoing.

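### The hepatitis B screening waiver can be met by evidence of no active infection alone, and no text shown makes a core antibody result a condition of using it

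*Protocol*

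**What the plan says.** In Amendment 1, Section 9.7.8.3 opens with the aim: "Subjects will be screened for evidence of previous or active hepatitis B or hepatitis C infection at Screening". It names the panel: "hepatitis B screening should include HBsAg, HBsAb, and HBcAb". The next sentence is the waiver. Subjects with documents from the 30 days before consent showing no active infection, "as measured by negative surface antigen or DNA for hepatitis B or negative RNA testing for hepatitis C", "do not need to repeat those tests during the screening period".

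The waiver appears in two other places:
- Table 9.1.1 footnote d, attached to the row for hepatitis B, hepatitis C and HIV: "Patients with documented negative results within the last 30 days do not need to be retested". The footnote's next sentence lists the three hepatitis B markers.
- Section 12.2 of the original protocol: "Screen for hepatitis B, hepatitis C, and HIV if required", with the three markers listed directly beneath. The Amendment 1 version of Section 12.2 is not in the supplied text.

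Exclusion criterion 9 (Section 9.3.2) bars chronic or active hepatitis B, shown by serology on the three markers "and confirmatory HBV DNA testing". It sends sites to the Laboratory Manual for interpretation. Past, resolved infection is not excluded.

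After infusion, Table 9.1.3 footnote g provides: "Testing for reactivation of hepatitis B and hepatitis C only for subjects with a past medical history of hepatitis B or hepatitis C". Table 9.1.6 footnote d and Section 9.4.8.2 apply the same restriction.

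**The concern.** The screening aim has two parts, previous and active infection, and the evidence that opens the waiver addresses only the second. A negative surface antigen or a negative DNA result does not show past infection. Among the tests listed, that needs the antibodies, HBcAb in particular.

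This matters because every subject takes prophylactic corticosteroids from Day 1, and the protocol times its hepatitis B rechecks to that exposure. The rechecks are reserved for subjects with a history. A past infection known to the subject should come out in the medical history at Screening. One that he does not know about can be found before dosing only by serology. If the serology is skipped, the subjects for whom the rechecks exist may not be identified.

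**Working it through.** No sample size, power or alpha figure is involved. The check sets the provisions side by side and counts the scheduled tests.

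**1. What the waiver requires.** One negative result suffices: surface antigen or DNA. Surface antigen is one of the three panel markers; DNA is not in the panel. Neither Section 9.7.8.3 nor footnote d lists an HBcAb result among the conditions.

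**2. What the waiver releases.** There are two readings.
- Narrow: only tests already done are excused. An HBcAb never measured cannot be repeated, so it remains due under the preceding sentence.
- Broad: the hepatitis B screen as a whole is satisfied. Listing DNA as qualifying evidence, and attaching footnote d to the whole row without saying which results must be negative, leave room for this.

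**3. What follows under the broad reading.** Section 9.4.8.2 sets the reactivation tests at 6 weeks after the start of corticosteroids, then at 1 and 13 weeks after completion. With the 19-week course of Section 9.1:
- first test: Week 6
- second test: 19 + 1 = Week 20
- third test: 19 + 13 = Week 32

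All three depend on a history of hepatitis B or C, so a subject with unrecognised past infection misses 3 of 3. Rechecks tied to later therapeutic courses carry the same restriction.

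**4. What remains for that subject up to Week 32.** Liver tests are weekly in Weeks 1-26 and then at Weeks 28, 30 and 32: 26 + 3 = 29 scheduled tests. Weekly cover runs 26 - 19 = 7 weeks beyond the course. An ALT rise leads to the work-up in Table 9.7.8.3.2, and the viral panel in Table 9.7.8.3.3 includes hepatitis B. This route starts only once ALT has risen. Section 7.4 reports ALT elevation in most treated subjects, so a rise does not in itself point to hepatitis B. From 1.5 to below 2 times baseline, a search for other causes is only to be considered; in the higher bands it is required.

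**5. A second gap.** The text shown does not say whether a positive HBcAb at Screening counts as a history. Even a fully screened subject might therefore be left out of the three tests, so correcting the waiver alone may not restore them.

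**The case against.** The strongest reply is that the ordinary reading leaves no gap. The waiver excuses repeating tests, and footnote d speaks of retesting. Both words presuppose a test already done. Footnote d, the original Section 12.2 and criterion 9 all name the three markers, so a site assessing criterion 9 as written is directed to HBcAb. The Medical Monitor approves each enrolment (Section 9.4.5). The Laboratory Manual, the steroid prescription guidelines cited in Section 9.4.8.2 and the Amendment 1 Section 12.2 are not shown, and any of them might require HBcAb outright. Harm needs a chain: the waiver used, the broad reading adopted, no HBcAb on record, an infection missed by the history, and no query at approval.

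Most of this stands. A reader might infer that the protocol exempts subjects from HBcAb, or lets DNA replace serology. The documents do not support either. The narrow reading is the more natural one, and a prior DNA result has its own use as the confirmatory test in criterion 9. What the reply does not supply is a sentence, in the text shown, that makes HBcAb a condition of the waiver. Medical Monitor approval does not name it either.

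**Conclusion.** The point holds as a minor safety improvement. The waiver's evidence does not match the screening purpose beside it, and the intended reading is left for sites to infer.

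For an affected subject the loss is three of three scheduled reactivation tests, with 29 liver tests and the ALT work-up remaining up to Week 32. That is conditional on the whole chain described above and says nothing about its likelihood. The number affected cannot be estimated, because the protocol gives neither the frequency of waiver use nor that of unrecognised past hepatitis B. Among about 20 subjects it would be few, possibly none. It would be wrong to infer that subjects will in fact go unscreened or that reactivation would go undetected.

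The conclusion assumes the planned 19-week course and that the documents not shown do not already require HBcAb. Power, the primary endpoint and its analysis are unaffected.

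**What to change.** In Section 9.7.8.3 and Table 9.1.1 footnote d, limit the waiver to each individual marker documented as negative within 30 days. HBsAg, HBsAb and HBcAb are then on record for every subject before infusion, and a DNA result does not stand in for serology. Add that a positive HBcAb at Screening counts as a history of hepatitis B for the reactivation tests. Check that the Amendment 1 Section 12.2 and the Laboratory Manual agree.

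The cost is about two sentences and a footnote edit, plus one serology assay on an existing screening draw for the few subjects who use the waiver.
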